## **8.5.2** Safety Analysis Populations

The ASaT population will be used for the analysis of safety data in this study. The ASaT population consists of all randomized subjects who received at least one dose of doubleblind study treatment. Subjects will be included in the treatment group corresponding to the study treatment they actually received for the analysis of safety data using the ASaT population. For most subjects this will be the treatment group to which they are randomized. Subjects who take incorrect study treatment for the entire treatment period will be included in the treatment group corresponding to the study treatment actually received. At least one laboratory or vital sign measurement obtained subsequent to at least one dose of double-blind study treatment is required for inclusion in the analysis of each specific parameter. To assess change from baseline, a baseline measurement is also required.

#### 8.6 **Statistical Methods**

#### 8.6.1 **Statistical Methods for Efficacy Analyses**

This section describes the statistical methods that address the primary objectives. Methods related to the exploratory objectives will be described in the sSAP.

The primary endpoint, percent change from baseline in LDL-C at Week 12, will be analyzed using a cLDA model proposed by Liang and Zeger. The model will include terms for treatment, time, risk category, and the interactions of treatment by time and time by risk category. This model assumes a common mean across treatment groups at baseline and a different mean for each treatment at each of the post-baseline time points. In this model, the response vector consists of baseline and the values (percent change) observed at each post-baseline time point. Time is treated as a categorical variable so that no restriction is imposed on the trajectory of the means over time. An unstructured covariance matrix will be used to model the correlation among repeated measurements. The cLDA model uses the maximum likelihood principle to estimate the parameters and account for missing data in an implicit fashion. The treatment difference in terms of mean percent change from baseline to Week 12 will be estimated and tested from this model to address the primary hypotheses. Sensitivity analysis will be performed to assess the robustness of the results to the assumptions about missing data. The details will be described in sSAP.

The above analysis based on restricted maximum likelihood (REML) assumes that the vector of model-based residuals follows a multivariate normal distribution. Under severe departures from normality, the REML-based analysis can be inefficient or potentially

MK-0653H-832-01 Final Protocol Confidential

**Protocol/Amendment No.:** 832-01

misleading. Accordingly, the residuals from the REML-based analysis, scaled by the inverse Cholesky root of the marginal variance-covariance matrix, will be subjected to a test for normality. If normality is not rejected at the  $\alpha$ =0.001 level, then the above REML-based analysis will serve as the primary analysis. However, if normality is rejected, then the primary analysis will be conducted using multiple imputation (MI) of missing values (if any) in conjunction with a robust regression approach that uses Mestimation. The model will include factors for treatment and risk category, and baseline value as a covariate. Of note, the 0.001 level for the normality test was chosen so that the default REML-based analysis is abandoned only under a clear departure from normality; moreover, this choice guarantees that there is no material inflation in the type I error rate for the treatment effect comparison due to a potential correlation between the test statistics for the treatment effect and the normality test.

The strategy to address multiplicity issues with regard to multiple treatment comparisons is described in Section 8.8, Multiplicity.

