## 8.1 Statistical Analysis Plan Summary

Key elements of the statistical analysis plan are summarized below; the comprehensive plan is provided in Sections 8.2-8.12.

Study Design	MK-0653H Phase III Factorial Study in Japanese				
Overview	Hypercholesterolemic Patients				
Treatment Assignment	Subjects will be randomized to the following 5 arms in a				
	1:2:2:2:2 ratio.				
	• EZ 10 mg				
	• Ros 2.5 mg				
	• Ros 5 mg				
	• MK-0653H (EZ 10 mg + Ros 2.5 mg)				
	• MK-0653H (EZ 10 mg + Ros 5 mg)				
	The study will be conducted as a double-blind study.				
Analysis Populations	Efficacy				
	Full Analysis Set (FAS) population, defined as all randomized				
	subjects who:				
	• received at least one dose of double-blind study treatment				
	• have baseline or post-baseline data				
	have baseline data for those analyses that require baseline				
	data.				
	Safety				
	All Subject as Treated (ASaT) population, defined as all				
	randomized subjects who received at least one dose of double-				
	blind study treatment.				
Primary Endpoint	Percent change from baseline in LDL-C at Week 12				
Statistical Methods for	Percent change from baseline in LDL-C at Week 12 will be				
Key Efficacy Analyses	analyzed using a constrained longitudinal data analysis				
	(cLDA) model proposed by Liang and Zeger  . The model				
	will include terms for treatment, time, risk category,				
	interactions of treatment by time and time by risk category.				
	The primary hypotheses will be evaluated by comparing MK-				
	0653H (EZ 10 mg + Ros 2.5 mg) to EZ 10 mg and to Ros 2.5				
	mg, as well as MK-0653H (EZ 10 mg + Ros 5 mg) to EZ 10				
	mg and to Ros 5 mg, based on the above model.				

**Protocol/Amendment No.:** 832-01

Statistical Methods for	Safety events of special interest such as elevations in liver		
Key Safety Analyses	function tests will be pre-specified as Tier 1 events. (Refer to		
	Section 8.6.2 for a full list of events.)		
	The Tier 2 events are as follows.		
	
 
AE
 
drug-related AE
 
		
	
 
serious AE (SAE)
 
drug-related SAE
 
		
	• discontinuation due to AE		
	discontinuation due to AE     discontinuation due to drug-related AE		
	discontinuation due to SAE		
	discontinuation due to SYE     discontinuation due to drug-related SAE		
	• specific AEs and system organ classes (SOCs) with		
	incidence $\geq 4$ subjects in at least one treatment group		

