## 8.9 Sample Size and Power Calculations

A total of 306 subjects will be randomized in a ratio of 1:2:2:2:2 to the following 5 arms: EZ 10 mg, Ros 2.5 mg, Ros 5 mg, MK-0653H (EZ 10 mg + Ros 2.5 mg), MK-0653H (EZ 10 mg + Ros 5 mg). Assuming that valid LDL-C measurements can be obtained at Week 12 from 31 subjects in the EZ 10 mg arm and from 62 subjects in each of the other 4 arms, the study will have a power of approximately 97% to successfully demonstrate both of the two families of primary hypotheses at  $\alpha$ =0.05, two-sided. For each of the two families of primary hypotheses, the study will have a power of approximately 97% that the family of primary hypotheses can be demonstrated at  $\alpha$ =0.025, two-sided. The study will have a probability of approximately 98% to show a numerically greater LDL-C percent reduction at Week 12 with MK-0653H (EZ 10 mg + Ros 5 mg) compared with MK-0653H (EZ 10 mg + Ros 2.5 mg). These calculations were performed using simulations. Power calculations for pairwise comparisons are shown in Table 6 below.

Table 6 Power Calculations for Pairwise Comparisons

Endpoint	N 1	$N_2$	Minimum detectable difference with 90% power $[\alpha=0.05 (0.025), \text{ two-sided}]$	Half-width of 95 (97.5) % CI	SD
LDL-C % change	62	62	9.4 (10.2) %	5.7 (6.5) %	16%
	62	31	11.5 (12.6) %	7.0 (8.0) %	16%

The calculations shown in Table 6, and the calculations above performed using simulations, are based on the assumptions on the true percent change from baseline in LDL-C at Week 12 for each treatment arm as shown in Table 7, and a true SD of 16%. These are conservative estimates from previously conducted factorial studies with EZ 10 mg and statins, as well as placebo-controlled monotherapy studies with EZ 10 mg or Rosuvastatin.

Table 7 Assumptions on True LDL-C Percent Change from Baseline by Treatment

Ezetimibe	Rosuvastatin			
Ezetimide	0 mg	2.5 mg	5 mg	
0 mg		-34%	-40%	
10 mg	-15%	-46%	-52%	

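### Does listing a treatment main effect in the primary cLDA model undo the common baseline mean and the baseline LDL-C adjustment?

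*Combined protocol and SAP*

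**What the plan says.** Section 8.6.1 gives the terms of the primary model: "The model will include terms for treatment, time, risk category, and the interactions of treatment by time and time by risk category". It follows at once with the mean structure: "This model assumes a common mean across treatment groups at baseline", and with separate treatment means at each later visit. It adds that "the response vector consists of baseline and the values (percent change) observed at each post-baseline time point", that "Time is treated as a categorical variable so that no restriction is imposed on the trajectory of the means over time", and that "An unstructured covariance matrix will be used to model the correlation among repeated measurements".

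Section 8.1 names the method as constrained longitudinal data analysis and repeats the list: the model "will include terms for treatment, time, risk category" and the two interactions. It does not repeat the sentence on the common baseline mean. It describes itself as a summary and refers to Sections 8.2 to 8.12 for the full plan.

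The fallback analysis, used if normality is rejected, adjusts for baseline openly: "The model will include factors for treatment and risk category, and baseline value as a covariate".

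**The concern.** In a constrained model the adjustment for baseline comes from the constraint. Baseline is a response, all arms share one baseline mean, and the unstructured covariance carries a chance baseline difference through to the Week 12 contrast. If each arm has its own baseline mean, that link is cut. With complete data the Week 12 contrast is then the plain difference in mean percent change, given risk category.

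Most software reads treatment, time and treatment by time as the saturated set, with a free mean for every arm at every visit, baseline included. Taken alone, the list in Sections 8.1 and 8.6.1 therefore describes an unconstrained model. If two models with different estimates and p-values could each claim to be the pre-specified primary analysis, the choice between them could be made after unblinding. The model read from the list alone would also be less precise and would leave chance baseline imbalance uncorrected.

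**Working it through.** **1. The plan's own figure.** Inputs from Section 8.9 and Table 7: 62 evaluable subjects per rosuvastatin or combination arm, SD 16%, and a 12-point difference in each rosuvastatin comparison (46 − 34 and 52 − 40).

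- SE = 16 × √(2/62) = 2.874, and 12/2.874 = 4.18.
- One comparison at 0.05: Φ(4.18 − 1.96) = 0.987. Both families: 0.987² ≈ 0.973. The two comparisons share no arm, and those with ezetimibe have power of about 1.
- One family at 0.025: Φ(4.18 − 2.24) = 0.973.
- Simulating the full Hochberg rule with t-tests (200,000 runs) gives 0.971 for both families, and 0.971 and 0.970 for each family.

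The stated 97% reproduces. It uses the unadjusted SD and takes no credit for baseline adjustment.

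**2. Counting mean parameters.** There are 5 arms, 4 time points (baseline and Weeks 4, 8 and 12) and 3 risk categories.

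- Listed terms, default coding: 5 × 4 + 2 × 4 = 28.
- Common baseline mean: 1 + 5 × 3 + 2 × 4 = 24.

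The 4 extra parameters are the between-arm differences at baseline. Numerical ranks of the design matrices were also 28 and 24.

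**3. Can the list and the constraint hold together?** Keep every listed term and set treatment to its reference level on baseline records. The rank falls to 24, and the Week 12 estimates equal those of the constrained model to within 10⁻¹¹. The two statements are compatible under that coding. Deleting the treatment main effect alone would not enforce the constraint, because a full treatment-by-time term still reaches the baseline visit.

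**4. The cost if the constraint were ignored.** Let ρ be the size of the correlation between baseline LDL-C and percent change. The documents do not give it, so the range 0 to 0.5 is an assumption. The constrained SE is 2.874 × √(1 − ρ²). A baseline imbalance of one standard error moves the unadjusted estimate by ρ × 2.874.

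| ρ (assumed) | SE, free baseline | SE, common baseline | Power for both families, common baseline | Shift per 1 SE of imbalance (points) |
|---|---|---|---|---|
| 0 | 2.87 | 2.87 | 97.1% | 0 |
| 0.1 | 2.87 | 2.86 | 97.3% | 0.29 |
| 0.2 | 2.87 | 2.82 | 97.7% | 0.57 |
| 0.3 | 2.87 | 2.74 | 98.3% | 0.86 |
| 0.4 | 2.87 | 2.63 | 99.0% | 1.15 |
| 0.5 | 2.87 | 2.49 | 99.5% | 1.44 |

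With a free baseline the power stays at the planned 97% in every row.

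Both models were also fitted to 300 simulated trials at each of three values of ρ, with 34 and 4 × 68 subjects and 1 − 279/306 = 8.8% missing at Week 12. Mean model SE, free versus common baseline, was 2.77 v 2.76 at ρ = 0, 2.76 v 2.70 at 0.2 and 2.76 v 2.54 at 0.4. Mean estimates were −11.99 v −11.99, −12.00 v −12.00 and −12.16 v −12.11, against a true −12. The free model estimated baseline differences of up to 9 to 11 mg/dL between two arms. The constrained model has none by construction.

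**5. Effect on conclusions.** A one-SE imbalance moves the test statistic by ρ. At the planned effect the statistic is 4.18 against a critical value of 1.96 or 2.24, a margin of at least 4.18 − 2.24 = 1.94.

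**The case for a change.** The strongest case for a change is that this text governs the primary model. Section 8.6.1 sends only exploratory methods and the missing-data sensitivity details to the supplemental SAP. Section 8.0 requires a protocol amendment to change primary methods. Section 8.10 uses the same model for subgroups, where arms are smaller and chance imbalance is larger. Section 8.1 gives the list without the sentence on the common mean, and neither section states how treatment is coded at baseline. The fallback model shows that baseline adjustment was wanted, and one clause would settle the matter.

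It stands that the list is loose and that default coding alone would give the wrong model. It does not stand that two analyses are equally pre-specified. A fit with free baseline means breaks an explicit sentence in Section 8.6.1 and is not a constrained analysis, so it could not be defended as the planned one. The fallback model counts the same way, since it confirms the intent that the sentence already states.

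The loss can be made to look larger. If noise in the baseline measurement is assumed to induce a correlation of 0.13 to 0.37, variance rises by 1/(1 − ρ²), or 2% to 16%. That corresponds to 279 × ρ², or about 5 to 38 completers. These figures rest on an assumed measurement CV of 6 to 10% and an assumed between-subject SD of 10 to 15 mg/dL. They also allow for no true relation between baseline and response, and they apply only if the constraint is ignored.

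**Conclusion.** No change follows. Section 8.6.1 names the method's defining constraint directly after the term list, and an analyst who follows the section in full fits the 24-parameter model with one common baseline mean. What is unwritten is how treatment is coded on baseline records, a detail that anyone fitting a cLDA model has to supply and that the text determines. Section 8.1 is a summary and does not override Section 8.6.1.

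Stating the coding would alter no planned estimate and no stated figure. Even under the misreading, no bias is expected under randomization, type I error is not expected to change, and the 97% power holds because it was computed with the unadjusted SD. The cost would be precision: an SE of 2.87 instead of 2.82 at ρ = 0.2 or 2.63 at ρ = 0.4, and nothing at ρ = 0. These sizes rest on the planning SD of 16%, 62 evaluable subjects per arm and an assumed ρ.

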# 6.0 TRIAL FLOW CHART

Phase	Screening (1~6 weeks)	Placebo run-in (2 weeks)	Treatment (12 weeks)		Follow up		
Week	Week -8~ -3¹	Week -2	Week 0	Week 4	Week 8	Week 12/ Discontinuati on	14 days after last dosing
Visit number	Visit 1	Visit 2	Visit 3	Visit 4	Visit 5	Visit 6	
Visit window permitted (Day) 	N/A	7~42+7	14+/-3	28+/-7	28+/-7	28+/-7	
Administrative procedure	1						
Obtain Informed Consent 	X						
Collect Medical History	X						
Review Inclusion/Exclusion criteria	X	X	X				
Review Prior/Concomitant Therapies	X	X	X	X	X	X	
Contact Patient Registration Center	X	X	X	X	X	X	
Risk assessment 	X	X	X				
Review Diet/Exercise and Instruct on JAS Guidelines	X						
Monitor Dietary/Exercise Compliance		X	X	X	X	X	
Dispense Study Drug 		X	X	X	X		
Randomized (assignment of randomization number)			X				
Monitor Medication compliance/patient diary			X	X	X	X	
Safety assessment							15
Review adverse event	X	X	X	X	X	X	X 15
Perform Physical Examination 		X				X	
Vital sign  Height/Weight 	X		X			X	
Sitting Blood Pressure/Pulse	X	X	X	X	X	X	
ECG		X					
Laboratory test 							
Lipid Panel A 	X	X	X	X	X	X	
hs CRP			X			X	
Apo protein (Apo) B			X	X	X	X	
Blood Chemistry 	X	X	X	X	X	X	
Hematology 	X					X	
TSH	X						
HbA1 C 	X					X	
Urinalysis 	X		X			X	
Pregnancy test 	X	X	X	X	X	X	

**Protocol/Amendment No.:** 832-01

1. Interval between Visit 1 and Visit 2 is determined depending on the presence of the prior treatments. Subjects washing out lipid-lowering therapy will have Visit 1 at -6 weeks from Visit 2; subjects not requiring washout will have Visit 1 at -1~-6 weeks from Visit 2 depending on the state of prior pharmacotherapy other than lipid-lowering agents in each subject.

- 2. Visit window is relative to previous Visit.
- 3. Informed consent must be obtained before any protocol-related study procedures are performed. It is allowable to obtain informed consent before Visit 1. After obtaining informed consent, subject will be given a unique screening number (refer to 7.1.1.6) and a subject identification card (refer to 7.1.1.3).
- 4. Subject's risk category assessment is determined at Visit 3 according to the Japan Atherosclerosis Society (JAS) Guideline 2012 based on the results obtained at Visit 1 and 2 (refer to Appendix 12.3).

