# 7.1.1.8 Trial Compliance (Medication/Diet/Activity/Other)

Adherence to study medication will be assessed by subject report by patient diary recorded by subject every day.

Interruptions from the protocol specified compliance <= 75% at each visit require consultation between the investigator and the Sponsor and written documentation of the collaborative decision on subject management.

Administration of trial medication at Visit 2 will be witnessed by the investigator and/or trial staff.

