# 7.1.2.3 Monitor Medication compliance

Subjects should be instructed to record date and the number of tablet/capsule that administered the study drug at home to the provided patient diary during treatment period. The site staff should confirm and collect the diary at each visit.

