#### 8.5 Analysis Populations

#### **8.5.1** Efficacy Analysis Populations

The FAS population will serve as the population for the analyses of efficacy data in this study. The FAS population consists of all randomized subjects who:

- received at least one dose of double-blind study treatment
- have baseline or post-baseline data
- have baseline data for those analyses that require baseline data.

**Protocol/Amendment No.:** 832-01

Even though no Per-Protocol analysis is planned, major deviations from the protocol that may substantially affect the results of the primary efficacy endpoint will be identified and documented in a separate memo prior to unblinding. Such major deviations include:

- off-drug periods during the treatment period
- noncompliance
- concomitant use of prohibited medications with presumed lipid lowering efficacy
- errors in assigned study medication during the study.

Subjects will be included in the treatment group to which they are randomized for analyses of efficacy data.

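### Does the normality-triggered switch to M-estimation in Section 8.6.1 change what the primary analysis estimates?

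*Combined protocol and SAP*

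**What the plan says.** Section 8.6.1 describes two branches.

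- **Default.** A cLDA model with an unstructured covariance. "The treatment difference in terms of mean percent change from baseline to Week 12 will be estimated and tested from this model".
- **Fallback.** The residuals, scaled by the inverse Cholesky root, are tested for normality at 0.001. "if normality is rejected, then the primary analysis will be conducted using multiple imputation (MI) of missing values (if any"). The plan applies this imputation step "in conjunction with a robust regression approach that uses Mestimation", with treatment, risk category and baseline in the model.

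The plan explains why it chose the 0.001 level: the default is left only on a clear departure from normality, and "this choice guarantees that there is no material inflation in the type I error rate for the treatment effect comparison" through correlation between the two test statistics. It does not name the normality test, the weight function or its tuning constant, or the imputation model.

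Section 8.5.1 analyses treated subjects as randomised and plans no per-protocol analysis. Among the deviations to be documented before unblinding it lists "off-drug periods during the treatment period".

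**The concern.** The default branch estimates a difference in means. M-estimation down-weights values far from the centre, so its contrast need not equal that difference. The data could then decide which of two quantities becomes the primary result, and the type I error statement in Section 8.6.1 does not address that.

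Subjects who stop taking drug but stay in the FAS are a plausible trigger. From Table 7, a 0% change lies 46 points from the EZ+Ros 2.5 mean but 34 from the Ros 2.5 mean (52 against 40 for the 5 mg pair). Such subjects can cause normality to be rejected, and are then discounted more in the combination arm, even if off-drug rates are equal.

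Monitoring does not exclude this. Section 7.1.1.8 says "Interruptions from the protocol specified compliance <= 75% at each visit require consultation", and Section 7.1.2.3 says "The site staff should confirm and collect the diary at each visit". In the flow chart "Visit window is relative to previous Visit", at 28 ± 7 days, so a lapse after Visit 5 may first be seen at Week 12. At stake would be the size and meaning of the reported effect.

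**Working it through.** **Inputs from Section 8.9.** Means: EZ −15, Ros 2.5 −34, Ros 5 −40, combinations −46 and −52. SD 16. Evaluable 31/62/62/62/62 (279) of 306 randomised, so dropout is 27/306 = 8.8%.

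**The plan's own figures.** Half-width for 62 v 62 is t × SD × √(2/n) = 1.98 × 16 × √(2/62) = 5.7, as in Table 6. The noncentral t gives a detectable difference of 9.39 (stated 9.4). Simulation with the Hochberg rule gives 97.2% power for both families (stated approximately 97%). Nothing in the sample size is wrong.

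**When the contrasts agree** (large samples, Ros 2.5 pair / Ros 5 pair):

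| Errors | Mean difference | Huber |
|---|---|---|
| Normal | −11.9 / −12.0 | −11.9 / −12.0 |
| Same skew in all arms | −11.9 / −12.0 | −12.0 / −12.0 |
| t(3) in combination arms only | −12.0 / −12.0 | −12.0 / −11.9 |

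A difference in shape is therefore not enough. It has to be asymmetric, or the contamination has to lie off-centre.

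**Size with off-drug subjects.** If a share p in both arms shows 0% change, the FAS mean difference is 12(1 − p): 11.64 at 3%, 11.4 at 5%. Discarding all such subjects would return 12, a move of 12p = 0.36 at 3%. The move can be somewhat larger because those in the Ros arm are discounted less.

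The full rule was simulated with assumptions that are not in the documents: within-subject correlation 0.7, Shapiro-Wilk, full loss of effect at Week 12 only, on-drug SD 16 or 13, Huber or bisquare weights.

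| Off drug | Switch rate, SD 16 / 13 | Shift, combination v Ros (points) |
|---|---|---|
| None, normal errors | 0.5% | none |
| 1% | 30 / 65% | 0.1–0.2 |
| 2% | 51 / 86% | 0.15–0.4 |
| 3% | 67 / 97% | 0.3–0.6 |
| 5% | 78 / 98% | 0.5–0.95 |
| 6% combination, 2% others | 84 / 99.7% | 0.9–2.0 |

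At 3% the largest shift is 0.6/5.7, about 11% of the half-width, and 0.6/12 = 5% of the planned effect.

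**Milder assumptions, 1% to 3% off drug.**
- 75% loss at Week 12: switch 3–13% / 22–48%, shift up to 0.35.
- Half loss: switch 0–2%, shift about 0.1 or less.
- Full loss at all visits: switch 2–4% / 7–27%.
- Anderson-Darling in place of Shapiro-Wilk: switch 0.2–3% / 1–15%.

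Partial loss is credible, since exclusion criterion 28 treats 6 weeks as the washout for most lipid-lowering drugs.

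**Consistency with SD 16.** Section 8.9 does not call its means on-drug values. Adding off-drug subjects to an on-drug SD of 16 gives √(16² + 0.03 × 0.97 × 46²) = 17.8 at 3% in EZ+Ros 2.5, above the plan's SD. With SD 13 the same formula gives 15.2 at 3% and 16.4 at 5%. In EZ+Ros 5, 5% gives √(13² + 0.05 × 0.95 × 52²) = 17.2. The largest shifts thus sit outside the plan's own variance assumption.

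**Coverage of the FAS mean difference.** Across 1%, 3%, 5% and 6% v 2% off drug, the rule as written covered in 93–96% of trials and cLDA alone in 93–97%. With 400 trials the Monte Carlo error is √(0.95 × 0.05/400) = 1.1 points.

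**Cost of removing the switch.** For one family at 0.025 under t(4) errors, cLDA with a sandwich SE has 96.6–97.1% power, against 99.4–99.7% for MI plus M-estimation. With 3% off drug it is 96.7–97.7% v 98.7–99.3% (SD 13) and 90–93% v 94–95% (SD 16); part of that gap is the shift itself.

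**The case for a change.** The strongest opposing case uses more extreme inputs. With 10% off drug in the combination arms and 2% elsewhere, the mean difference of about −8 becomes −9.5 to −10.2 at SD 16, and as far as −11.5 at SD 12 with bisquare weights. With skewed errors in the combination arms only and a true mean difference of zero, one-sided rejection at nominal 2.5% was 12.7% under the two-stage rule, against 3.0% by means. Pre-specification does not tell a reader which effect the headline number describes, and the switch rate depends heavily on a normality test that the plan does not name.

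Part of this stands. The contrasts can differ, and the justification in Section 8.6.1 does not cover a change of target. The error rate of the two-stage rule with unequal off-drug rates and equal FAS means was not computed.

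The extreme inputs have no basis in the documents, however. If ezetimibe added nothing to rosuvastatin, the natural expectation is the same error shape in both arms. With skew in all arms, normality was rejected every time and the two-stage error was 2.4%. Off-drug rates are also held down by the requirement of more than 75% run-in compliance (inclusion criterion 10), discontinuation for serious deviation (Table 2) and consultation on low compliance. Section 8.11 reports compliance by arm, so an imbalance would be visible.

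**Conclusion.** No change follows. The mechanism is real but narrow: it needs asymmetric contamination that sits differently against the arm means. At 1% to 3% off drug with full loss at Week 12 only, it moves the contrast by 0.1 to 0.6 points on an effect of about 12; with half loss, by about 0.1 or less. The superiority conclusion is unlikely to change, type I error is not materially inflated when off-drug rates are equal, and intervals still cover the FAS mean difference about as well as cLDA alone.

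The fallback is a fair trade-off: fixed in advance, rarely used under normal errors, and worth about 3 points of power under t(4). The unnamed test, weight function and imputation model are details that a trial statistician would settle before unblinding. If the switch occurs, the clinical study report can show the cLDA mean difference beside the robust estimate without altering the rule.

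These sizes rest on assumed off-drug rates, correlation, timing of the loss and choice of normality test, none of which the documents give. A much higher and strongly unequal off-drug rate would make the gap larger.
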